Subjects who complete Phase A will be eligible to enter the extension phase, Phase B, for an additional 52 weeks of treatment. Subjects will remain on their randomized treatment (SM04690 or placebo) for the additional year. Each subject that consents to enter Phase B will receive an injection at Week 52 (EOSa) and Week 76 with follow-up clinic visits scheduled at Weeks 64, 76, 88, and 104 (EOSb) or ET. Specific timing of protocol procedures is described in the Schedule of Events Table ([Section 7.3.7](#)). Specific timing of electronic diary and questionnaire

completion is described in the Schedule of Electronic Diary and Questionnaire Completion Table (Section 7.3.8).

Primary analysis of Phase A data will be completed after the last subject completes Week 52 (EOSa). While the Sponsor will be unblinded to study treatment after the Phase A analysis (after the last subject completes Week 52 [EOSa]), the Investigator and the subject will remain blinded.

In Phase B, qCT will be performed at Weeks 64, 76, 88, and 104 (EOSb) or ET. DXA will be performed at Weeks 76 and 104 (EOSb) or ET. Bone and cartilage biomarkers will be assessed at Weeks 64, 76, 88, and 104 (EOSb) or ET. Radiographic images of the knees will be performed at Weeks 76 and 104 (EOSb) or ET.

Subjects will be required to complete the following:

- Daily pain NRS
- Monthly completion of the WOMAC
- Monthly completion of Patient Global Assessment

Recording of signs and symptoms of study medication intolerance and AE reporting will start following the first injection of the study medication and continue until the subjects complete their last study visit. All AEs, whether volunteered, elicited, or noted during examination, will be recorded throughout the study.

Subject Re-Screening

Subjects are allowed to be re-screened once. Re-screens are limited to subjects who did not meet inclusion/exclusion criteria due to a transient reason. Transient refers to self-limiting and predictably resolving conditions or acute events (e.g., common cold or otitis media), reversible medical conditions that are successfully treated (e.g., anemia successfully treated by infusion), and/or being unable to comply with study procedures due to administrative convenience (e.g., family issues or attending to a private matter). Diary non-compliance is not a transient event and subjects with diary non-compliance may not be re-screened.

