5.5.2 HANDLING OF PARTICIPANT WITHDRAWALS OR TERMINATION

In case of premature discontinuation of study participation, ET procedures should be conducted within 14 days of discontinuation for any subject who discontinues after the Day 1 visit, if possible. The date the subject is withdrawn from the study and the reason for the discontinuation should be recorded on the eCRF. The Investigator or designee must complete all applicable eCRF pages for subjects who discontinue from the study prematurely.

Replacement of subjects who withdraw or discontinue prematurely is not allowed.

Subjects who are withdrawn from study medication for safety reasons will continue with all planned study visits per protocol, without any further dosing.

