6.1.9 DURATION OF THERAPY

The injectable investigational product or placebo is to be administered as a single intra-articular injection into the target knee joint once each at Day 1 and Week 24 (Phase A), and once each at Week 52 (EOSa) and Week 76 (Phase B).

At the Week 24, 52 (EOSa), and 76 visits, the Investigator should evaluate the subject for suitability to receive the study medication injection. The subject should not have any condition, including laboratory findings and findings in pre-injection assessments, that, in the opinion of the Investigator, constitutes a risk or contraindication for the injection, or that could interfere with the study objectives, conduct, or evaluation. The injections may occur up to two weeks later than the Week 24, 52 (EOSa), and 76 visits, respectively, to allow for resolution of any intercurrent illness (e.g., infection) prior to the injection. If, in the opinion of the Investigator, the subject should not receive any of the injections, the subject will discontinue treatment but will continue with all planned study visits per protocol.

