3.2.7 Phase B Efficacy Endpoints

1. Characterization of change in OA pain in the target knee as measured by the weekly averages of daily pain NRS from baseline through Week 104 accounting for repeated injections
2. Characterization of change durability of treatment response in OA pain in the target knee as measured by the weekly averages of daily pain NRS through Week 104 elapsed from prior injection to repeat injection
3. Characterization of change in OA function in the target knee as measured by WOMAC Function from baseline through Week 104 accounting for repeated injections
4. Characterization of change durability of treatment response in OA function in the target knee as measured by WOMAC Function through Week 104 elapsed from prior injection to repeat injection
5. Characterization of change in mJSW as measured by radiograph of the target knee from baseline through Week 104 accounting for repeated injections
6. Characterization of change durability of treatment response in mJSW as measured by radiograph of the target knee through Week 104 elapsed from prior injection to repeat injection
7. Characterization of change in OA pain in the target knee as measured by WOMAC Pain from baseline through Week 104 accounting for repeated injections
8. Characterization of change durability of treatment response in OA pain in the target knee as measured by WOMAC Pain through Week 104 elapsed from prior injection to repeat injection
9. Characterization of change in OA disease activity as measured by Patient Global

Assessment from baseline through Week 104 accounting for repeated injections

10. Characterization of change durability of treatment response in OA disease activity as measured by Patient Global Assessment through Week 104 elapsed from prior injection to repeat injection

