7 ANALYSIS POPULATIONS

7.1 Full Analysis Set

The Full Analysis Set (FAS) includes all subjects who were randomized and received at least one study injection. The FAS is used to describe the analysis set which is as complete as possible and as close as possible to the intent-to-treat ideal of including all randomized subjects. Subjects will be analyzed as randomized for the FAS.

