7.2 Full Analysis Set Phase B

The Full Analysis Set Phase B (FASB) includes all FAS subjects who received at least one study injection in Phase B. Subjects will be analyzed as randomized for the FASB.

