8.1.3 Mixed-Effects Models for Repeated Measures

A mixed-effects model for repeated measures (MMRM) will be used to analyze change over time in Pain NRS. The model will be estimated assuming a Toeplitz variance-covariance matrix. The Toeplitz structure is a more generalized form of autoregressive-1 (AR1) structure, allowing the data to inform how the correlation between within-subject observations decreases over time instead of implicitly defining a uniform decay structure (Kincaid, 2005).

MMRM presumes that missing data are not caused by something observable within the conduct of the trial (i.e. missing-at-random [MAR]). It is plausible to presume a MAR mechanism as there have been no observed tolerability issues to the administration of study injection during the prior development trials. Additionally, the study injection cannot be removed after it has been administered, eliminating study drug discontinuation as a source of treatment estimate confounding.

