12 EFFICACY ANALYSIS

A statistical description of Pain NRS at baseline will be provided along with absolute changes from baseline at each subsequent timepoint for subjects in the FASB and PPASB. Statistical descriptions of WOMAC Pain, WOMAC Function, Patient Global Assessment, and mJSW at baseline will also be provided along with absolute changes from baseline at each subsequent timepoint for subjects in the FASB only.

Changes in the target knee from baseline in Pain NRS will be characterized using MMRM for subjects in the FASB and PPASB; the models will be evaluated through Week 104 (EOSb). All models will use treatment group, week, treatment×week interaction, and baseline values as covariates. Unadjusted 95% confidence intervals and P values will be reported.

If a subject submitted data related to their non-target knee due to an electronic device error, this data will not be analyzed.

Subject-level listings will be provided.

Since Phase A analysis (defined prior to unblinding) was the primary analysis for this study, there will be no estimands provided for Phase B.

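### The only Phase B efficacy model uses only subjects injected in Phase B, so its Week 104 arm contrast is conditional on a post-randomisation event; no FAS version is planned

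*SAP*

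**What the plan says.** The first Phase B efficacy endpoint in SAP 3.2.7 concerns "weekly averages of daily pain NRS from baseline through Week 104 accounting for repeated injections". SAP 8.1.1 keeps the Phase A baseline for Phase B.

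SAP 12 plans one efficacy model: "Changes in the target knee from baseline in Pain NRS will be characterized using MMRM for subjects in the FASB and PPASB". Its terms are treatment, week, treatment by week and baseline, and unadjusted 95% intervals and P values are reported. WOMAC Pain, WOMAC Function, Patient Global Assessment and mJSW are described in the FASB without a model.

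The FASB "includes all FAS subjects who received at least one study injection in Phase B" (SAP 7.2). The PPASB (SAP 7.5) additionally requires Phase A per-protocol status and completion of Phase B. Under Protocol 4.1 only Phase A completers are eligible, and consent is needed: "Each subject that consents to enter Phase B will receive an injection at Week 52 (EOSa) and Week 76". Protocol 6.1.9 adds an Investigator suitability check before each later injection.

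The FAS is described in SAP 7.1 as "as close as possible to the intent-to-treat ideal of including all randomized subjects", yet SAP 12 gives it no role.

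On missing data, SAP 8.1.3 says: "MMRM presumes that missing data are not caused by something observable within the conduct of the trial". It equates this with missing at random (MAR). It adds that, because an injection cannot be taken back, stopping study drug is ruled out as a source of confounding.

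**The concern.** The model spans the whole randomised comparison, from baseline to Week 104, but is fitted to a subset chosen by what happened after randomisation. If pain influences who goes on, and does so differently in the two arms, the entrants' Week 104 difference is not the difference between the randomised groups.

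A repeated-measures likelihood model can use the earlier pain of subjects who leave to adjust for their absence, but only if those subjects are in the model. Here they are removed, so the MAR argument applies only to data lost after entry. The exclusion could also reach scores collected after Week 52. Protocol 5.5.2 says subjects withdrawn from study medication for safety reasons "will continue with all planned study visits per protocol, without any further dosing", and Protocol 6.1.9 says that when an injection is withheld "the subject will discontinue treatment but will continue with all planned study visits per protocol". Anyone followed this way with no Phase B injection is outside the FASB.

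SAP 8.1.3 does not fill the gap. MAR allows missingness to depend on observed data, which the SAP's sentence denies. Four injections are scheduled (SAP 14.2) and later ones can be withheld, so stopping treatment is not eliminated.

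At stake is a Week 104 estimate with a P value that could be read as a comparison of randomised arms, with bias possible in either direction.

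**Working it through.** **Analysis sets used through Week 104 in this SAP**

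| Outcome | Method | Set |
|---|---|---|
| Knee, spine and hip BMD (SAP 11) | ANCOVA | SAS, identical to FAS per SAP 7.6 |
| Biomarkers (SAP 13) | ANCOVA | SAS for the summaries; no other set named for the model |
| Pain NRS (SAP 12) | MMRM | FASB, PPASB |
| Other efficacy (SAP 12) | Descriptive | FASB |

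Efficacy is the exception, and no reason is given.

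**The plan's own figure.** The only power figure is 81.6% for the BMD ratio (SAP 6). With log-scale SD = sqrt(ln(1 + 0.30²)) = 0.2936, difference ln(0.93/0.80), 50 per arm and one-sided 0.05, the non-central t (98 df) gives 81.6%. It reproduces, but has no bearing on Pain NRS.

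**Size of the possible bias.** The documents give no entry rate, SD or correlation, so everything here is assumed: pain has SD 1, the true arm difference is -0.50 (lower is better), the Week 52-104 correlation is 0.7, and entry is logistic in Week 52 pain with slope 1 (2 for the strong rule), higher pain making entry less likely.

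Let d be the mean Week 52 pain of entrants minus that of everyone in the arm. Then

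FASB estimate = -0.50 + 0.7 × (d_active - d_placebo).

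Numerical integration gives d = -0.213, -0.173 and -0.091 at 75%, 80% and 90% entry. If only placebo entry is pain-driven at 75%: -0.50 + 0.7 × 0.213 = -0.351. If only active entry is: -0.50 - 0.7 × 0.213 = -0.649. For a common rule averaging 75% entry, d_placebo = -0.245 and d_active = -0.181, so -0.50 + 0.7 × 0.063 = -0.456. For the strong common rule, d is -0.385 and -0.251, giving -0.406.

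A simulation (300,000 per arm, 8 equally spaced visits, all data after Week 52 missing for non-entrants) also fitted a Toeplitz model to the FAS by maximum likelihood:

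| Entry mechanism | Entry, placebo / active | FASB, integration | FASB, simulation | FAS, simulation |
|---|---|---|---|---|
| Same entry rate and slope in both arms | 75% / 75% | -0.500 | -0.496 | -0.497 |
| One pain rule for both arms | 71% / 79% | -0.456 | -0.455 | -0.498 |
| Strong common rule | 69% / 81% | -0.406 | -0.406 | -0.497 |
| Pain-driven in placebo only | 75% each | -0.351 | -0.348 | -0.500 |
| same | 80% each | -0.379 | -0.376 | -0.498 |
| same | 90% each | -0.436 | -0.438 | -0.501 |
| Pain-driven in active only | 75% each | -0.649 | -0.651 | -0.502 |
| same | 80% each | -0.621 | -0.622 | -0.500 |
| same | 90% each | -0.564 | -0.564 | -0.502 |

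When the true covariance is not Toeplitz (SD rising from 0.8 to 1.0, or random slopes), the FAS estimates run from -0.471 to -0.533.

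**Against sampling error.** With 75% of 50 = 37.5 per arm, SE = sqrt(2/37.5) = 0.231 SD. Coverage of a 95% interval with bias b is Φ(1.96 - b/SE) - Φ(-1.96 - b/SE): 94.6% at b = 0.045, 93.1% at 0.094 and 90.0% at 0.15.

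**On the NRS scale.** A separate two-timepoint simulation with no true difference, an assumed SD of 2.0, correlation 0.5 to 0.85 and entry of 60% to 90% gave a spurious entrants-only difference of 0 to about 0.75 points. A likelihood estimate that kept non-entrants' Week 52 scores stayed within 0.01 of zero.

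**The case against.** The strongest reply is that this is a supportive analysis in a trial with no formal hypothesis test (Protocol 10.2), and that Phase B has no estimands (SAP 12). Protocol 10.4.3 plans a Pain NRS model through Week 52, so non-entrants' Phase A pain is not lost to the study; the separate Phase A SAP, not available here, may use the FAS. The protocol assigns no analysis set to the efficacy models, so the FASB contradicts nothing in it, and the set's name says Phase B. All of this is fair and limits the severity. It does not say whom the Week 104 P value describes.

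Second, the 0.15 SD figure is a worst case. Subjects and Investigators stay blinded, the suitability check is not about pain level, and entry may reflect other things, such as enrolment before the extension was added. This stands: bias is possible, not shown, and a rule shared by both arms gives 0.04 to 0.09 SD. Nor do the documents show that anyone was followed past Week 52 without a Phase B injection.

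Third, the FAS model performs well partly because entry was simulated to depend only on observed Phase A pain. With a misspecified covariance its error (up to 0.033 SD) approaches the smallest bias it would remove, and it was not tested with about 100 subjects and 104 weekly scores. That is a reason to show both results. The planned FASB model has the same weekly structure and fewer subjects.

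Fourth, selection would be partly visible from listings, or by setting the FASB Week 52 contrast beside the Phase A one. The SAP plans no such comparison. The by-arm disposition table (SAP 9.1) would show unequal entry rates, but not pain-driven entry in one arm at equal rates, which gives the largest bias here.

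**Conclusion.** The concern holds. SAP 12 restricts its only efficacy model to sets defined by post-randomisation events, leaves out randomised and treated subjects with observed pain, plans no FAS version, and does not label the contrast as conditional on Phase B entry. SAP 8.1.3 misstates MAR and wrongly treats discontinuation as eliminated; that wording error stands whatever the size of the bias.

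The bias is zero when selection is the same in both arms and up to about 0.15 SD, in either direction, in the one-arm cases examined. These figures rest on one assumed true effect, a correlation of 0.7, slopes of 1 or 2 and the entry rates shown. The text is certain; the existence and direction of bias in this trial are unknown. The plan should be changed, but the issue does not reach the primary Phase A analysis.

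**What to change.** - **SAP 12:** fit the same Pain NRS MMRM to the FAS as well, using all weekly scores from Week 1 to Week 104, including those of subjects who did not enter Phase B. Report its Week 104 contrast beside the FASB and PPASB results, and label those two as conditional on Phase B entry.
- **SAP 9.1:** add a table of Week 52 Pain NRS by arm and Phase B entry status, so that selection at equal entry rates can be seen.
- **SAP 8.1.3:** state that MAR allows missingness to depend on observed data, and delete the claim that stopping study drug is eliminated.

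The cost is SAP wording, one rerun of a specified model on a set already defined, and one small table. The downside is that Week 104 values for non-entrants rest on MAR extrapolation and the Toeplitz covariance, and describe pain as if those subjects had continued like similar entrants. That is a different question from the FASB one, so both results should be shown.

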13 EXPLORATORY BIOMARKER ANALYSIS

A statistical description of biomarkers COMP, P1NP, and β -CTX at baseline will be provided along with absolute and percent changes from baseline at each subsequent timepoint for subjects in the SAS.

Baseline-adjusted ANCOVA will also be used to analyze the change from baseline in these biomarkers and evaluated at Weeks 4, 12, 24, 36, 52 (EOSa), 64, 76, 88, and 104 (EOSb). Subject level listings will be provided.

14 MEDICATIONS

The summary of medications will be performed on the SASB.

14.1 Concomitant Medications

The World Health Organization Drug Dictionary (WHODD) will be used to classify prior and concomitant medications by Anatomical Main Group (Anatomical Therapeutic Chemical, ATC, Level 1), Therapeutic Subgroup (ATC Level 2), and preferred term. Prior and concomitant medication usage will be summarized by the number and percentage of subjects receiving each medication by treatment group.

The subgroup of medications initiated after Week 52 injection will be summarized in the same manner. If a medication start date is incomplete, it will be imputed with the latest possible date to increase the likelihood it is included in the table of medications initiated after first exposure. For example, medication start dates of “2019” and “2020-02” would be imputed to “2019-12-31” and “2020-02-29”, respectively.

Subject-level listings containing prior and concomitant medications (WHODD coding), and procedures/non-drug therapies (MedDRA coding) will be provided and will display the dates as they were entered (not the imputed version described above).

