11. SOURCE DOCUMENTS AND ACCESS TO SOURCE DATA/DOCUMENTS

The Investigator must maintain required records for all study subjects. Source data are all information, original records of clinical findings, observations, or other activities in a clinical trial necessary for the reconstruction and evaluation of the trial. Source data for this study will be recorded in the subject's source documents and on the eCRFs. All data on these eCRFs should be recorded completely and promptly. A copy of the completed eCRFs for each subject will be retained by the investigational center.

The Investigator must maintain adequate and accurate source documents upon which eCRFs for each subject are based. They are to be separate and distinct from eCRFs, except for cases in which the Sponsor has predetermined that direct data entry into specified pages of the subject's eCRF is appropriate (e.g., eCOA questionnaires). The source documents should include detailed notes on the following:

- The oral and written communication with the subject regarding the study (including the risks and benefits of the study); the date of informed consent(s) must be recorded in the source documentation

- The subject's medical and disease history before participation in the study
- The subject's basic identifying information, such as subject number, that links the subject's source documents with the eCRFs
- The results of all diagnostic tests performed, diagnoses made, therapy provided, and any other data on the condition of the subject
- All AEs (All AEs may be documented in the source document but only those defined in the protocol will be transferred to the eCRFs)
- The subject's exposure to any concomitant therapy (including start and stop dates, route of administration, and dosage) (All concomitant therapies may be documented in the source document but only those defined in the protocol will be transferred to the eCRFs)

ePRO questionnaire data is considered electronic source data created as subjects enter responses into the electronic device. Once submitted, responses cannot be changed or modified by the subject or any other user. There is no source data verification required for such data as is it directly attributable to the subject once electronically stored. Therefore, eCOA questionnaire results are not transferred to eCRFs.

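### SAP 14.1 moves incomplete medication start dates as late as possible without stopping at the recorded stop date, so a drug finished before the Week 52 injection can be counted as new in Phase B

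*SAP*

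**What the plan says.** SAP 14 sets the population for the medication tables: "The summary of medications will be performed on the SASB", that is, subjects with at least one Phase B injection. SAP 14.1 first summarises all prior and concomitant medication, then adds a second table: "The subgroup of medications initiated after Week 52 injection will be summarized in the same manner".

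The dating rule follows directly: "If a medication start date is incomplete, it will be imputed with the latest possible date". Its stated purpose is "to increase the likelihood it is included in the table of medications initiated after first exposure". Two examples are given, a year-only start in 2019 and a year-and-month start in February 2020, which "would be imputed to “2019-12-31” and “2020-02-29”, respectively". Both use the start entry alone, and no stop date enters either one. Neither the SAP nor the protocol limits the imputed start to the stop date.

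The listings are separate from this rule. They "will display the dates as they were entered (not the imputed version described above".

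On what is collected, Protocol section 11 asks that source documents hold "The subject's exposure to any concomitant therapy (including start and stop dates, route of administration, and dosage". Protocol section 7.5 lists the items for the medication eCRF page (name, indication, route, dose and frequency) and mentions neither dates nor the visit at which a drug was first recorded.

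**The concern.** Two things do not fit together in SAP 14.1.

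First, the cut-off. The table is defined by the Week 52 injection, but the reason for the imputation speaks of drugs "included in the table of medications initiated after first exposure". First exposure is the Day 1 injection. Under a Day 1 cut-off, pushing an uncertain date late moves mainly pre-study drugs into the on-treatment table. Under a Week 52 cut-off, a full year of Phase A records lies on the earlier side of the line, and the same push moves Phase A drugs into a Phase B table.

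Second, the missing limit. A drug cannot start after it stopped, yet the rule as written can produce such a record and then count it as a Phase B initiation.

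At stake is the accuracy of the one planned summary of drugs newly started in the second year. A reader may turn to it to see whether new concomitant treatment differed between the arms in Phase B.

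**Working it through.** **Inputs.** The imputation rule, its two examples and the Week 52 cut-off come from SAP 14.1. The estimated first consent (November 2018) and last completion (October 2021) come from the Protocol Summary. The minimum screening period of 10 days, Week 52 at Day 365 and Week 104 at Day 729 come from Protocol section 7.3. The drug records below are invented for illustration and are not trial data.

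**Step 1: reproduce the SAP's examples.** Year only gives 31 December; year and month gives the last day of that month. Hence 2019 becomes 2019-12-31, and 2020-02 becomes 2020-02-29 (a leap year). Both agree with the SAP.

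**Step 2: when the rule can go wrong.** Let the incomplete entry allow true starts from date a to date b, let J be the Week 52 injection and E the recorded stop. The imputed start is b, and the drug is counted if b > J. The count is wrong when the true start is on or before J, so an error requires a ≤ J < b: the incomplete period must contain the injection and end after it. If in addition E < J, the count is certainly wrong, and the imputed start b falls after E.

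**Step 3: where Week 52 falls.**
- Earliest: 1 November 2018 + 10 days = 11 November 2018 (Day 1); + 364 days = 10 November 2019.
- Latest: 729 − 365 = 364 days before a last visit between 1 and 31 October 2021, which is 2 October to 1 November 2020.

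The injection may follow the visit by up to two weeks (Protocol 6.1.5). A year-only 2020 entry, imputed to 31 December 2020, therefore falls after every expected Week 52 injection.

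**Step 4: worked records, as written and with the cap min(b, E).**

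| Start entered | Stop | Week 52 injection | Imputed as written | Counted? | With cap | Counted? |
|---|---|---|---|---|---|---|
| 2020 | 2020-03-10 | 2020-08-14 | 2020-12-31 | yes | 2020-03-10 | no |
| 2020-02 | 2020-02-06 | 2020-02-10 | 2020-02-29 | yes | 2020-02-06 | no |
| 2020 | ongoing | 2020-08-14 | 2020-12-31 | yes | 2020-12-31 | yes |
| 2019 | any | 2020-02-10 | 2019-12-31 | no | not later | no |
| 2020-02 | any | 2020-08-14 | 2020-02-29 | no | not later | no |

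In row 1 the imputed start is 366 − 70 = 296 days after the stop (10 March is day 70 of 2020); in row 2 it is 29 − 6 = 23 days after. Rows 1 and 2 are the defect. Row 3 is untouched by the cap. Rows 4 and 5 are classified correctly under the rule as it stands.

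**Step 5: a ceiling on the share affected.** The documents give no count of incomplete dates. Assume the true start is uniform over the incomplete period. Among entries that span the injection, the share that began on or before it is (J − a + 1)/(b − a + 1):
- Year only, injection 10 February 2020: 41/366 = 11%
- Year only, 15 June 2020: 167/366 = 46%
- Year only, 14 August 2020: 227/366 = 62%
- Year only, 15 October 2020: 289/366 = 79%
- Year only (2019 entry), 15 December 2019: 349/365 = 96%
- Year and month, 10 February 2020: 10/29 = 34.5%
- Year and month, 15 June 2020: 15/30 = 50%

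These are shares of the spanning incomplete entries, not of the table. They are also ceilings for what the cap corrects, because only drugs that both began and stopped before the injection are removed.

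**Step 6: weight of one subject.** With about 50 randomised per arm (SAP 6), and no more than that in the Phase B safety set, one wrongly counted subject moves a drug's percentage by at least about 1/50 = 2 points, provided the subject has no genuine Phase B start of the same drug.

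**The case against.** The strongest reply is that leaning towards inclusion is deliberate and disclosed: the SAP says it wants uncertain drugs in the table. That stands. Counting an ongoing drug with an uncertain start as new is a defensible cautious choice, and preferring a shorter table would be taste. The choice does not extend to a drug known to have ended before the injection, because its start is not uncertain with respect to the cut-off.

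It can also be said that a latest possible date already implies a date no later than the stop. That is a fair reading, but the SAP does not state it and both examples are worked from the start entry alone, so a programmer following the text would not apply it.

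The consequences are limited in several ways, and all of these hold. The table is descriptive, no Pain NRS or bone density model uses it, the rule is the same in both arms, and the listings show the entered dates. Prohibited medication is handled as protocol deviations, and those not tied to a visit are dated from monitors' comments against the Week 52 injection (SAP 9.2), with no reference to imputed dates.

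A reader might infer that Phase A drugs in general are counted as Phase B starts, or that the table will be filled with them. The documents do not support this: only incomplete dates that span the injection are exposed, and their number is nowhere given. Nor do they give this table a role in explaining pain or bone density results.

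**Conclusion.** The point holds as a minor defect. Followed literally, SAP 14.1 can assign a start date after the recorded stop date and count a drug that ended before the Week 52 injection as newly started in Phase B. The stated reason for the rule also names a different cut-off from the table it serves.

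The absolute size cannot be computed. The shares of 11% to 96% for year-only entries depend on the protocol's estimated calendar and on uniform true starts, and they bound only an unknown and possibly small set of records. They should not be read as an error rate for the table. Drugs with incomplete starts that were ongoing at, or stopped after, the injection remain in the table by the SAP's own choice, and that is not part of the defect. No efficacy or bone density estimate changes.

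**What to change.** In SAP 14.1, state that an incomplete start date is imputed to the latest possible date but no later than the recorded stop date, and replace the reference to first exposure with the Week 52 injection.

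This assumes that stop dates are available in the analysis data. Protocol section 11 requires them in source documents; the list of eCRF items in section 7.5 does not mention them, so this should be confirmed.

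Optionally, if the database stores the visit at which a drug was first recorded, drugs first recorded before the Week 52 injection can be treated as started before it. This would also deal with Phase A drugs that continued past the injection. The documents do not show that such a field exists, so the main fix should not depend on it.

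The cost is one clause, one wording correction and one programming condition. The table will hold slightly fewer drugs.
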